7.2.2 Safety assessment

The safety assessments will be based on the following: Adverse Events (AEs), injection site tolerance, clinical laboratory parameters (blood), vital signs. A central laboratory will be used to analyze and report blood chemistry/hematology. eGFR would also have been evaluated locally only for screening. eGFR evaluated centrally will be used for safety evaluation.

- **Adverse events**

Adverse Event monitoring will be recorded until Day+1. After, AEs that the investigator considers related to P03277 and/or study procedures will be recorded at optional V4.

- **Injection-site tolerance**

For all subjects, injection-site tolerance (burning, pain, eruption, extravasation, inflammation, or other) will be assessed over 1 day following each contrast agent injection (during the injection up to 30 ± 5 mn, and the day after injection) and over a longer period if the investigator becomes aware of any related AE. In case of injection-site pain, the subject will be asked to specify the level of pain using a visual analogic scale (VAS, [REDACTED]) from 0 (no pain) to 10 (maximal pain).

- **Clinical laboratory parameters**

For each subject, blood samples will be performed at baseline and Day+1 for being analyzed by a central laboratory.

The following parameters will be obtained and assessed:

- Hematology: Red Blood Cells (RBCs), White Blood Cells (WBCs), neutrophils, eosinophils, basophils, lymphocytes and monocytes, platelet count, hemoglobin, hematocrit, Mean red blood Cells Volume (MCV).
- Biochemistry: sodium, potassium, chloride, random glucose, Blood Urea Nitrogen (BUN) / urea, creatinine, eGFR, Cystatin C, total protein, calcium, phosphorus, total bilirubin, unconjugated and conjugated bilirubin, Aspartate Amino Transferase (AST), Alanine Amino Transferase (ALT), alkaline phosphatase, Lactate DeHydrogenase (LDH). Triglycerides (TG).

In female subjects of childbearing potential, a urine or serum pregnancy test will be performed on-site prior to the administration of IMP.

For all other laboratory assessments, the central laboratory will flag laboratory values falling outside of the normal ranges on the central laboratory report (which the investigator should review and sign off) and the investigator will report any values considered clinically significant as an AE or alternatively according to investigator's judgement as medical history if measured at baseline and related to an underlying disease.

Guerbet  CONFIDENTIAL	Protocol No. GDX-44-008 Version No.4.0 including amendments 1 and 2 12 December 2017	Page 35 / 64
--	--	--------------

- **Vital signs**

Vital signs (systolic and diastolic blood pressure in supine position, pulse rate) will be measured and recorded according to the following schedules:

- Immediately prior to each contrast agent injection (baseline value)
- At 30+-5 minutes following P03277 injection
- One day after P03277 injection

If significant changes in vital signs occur, vital signs should be recorded more frequently, and for as long as necessary, to ensure that the changes have been resolved and/or that the subject is stable. All clinically significant abnormal value or change value will be recorded as AEs or alternatively according to investigator's judgement as medical history if measured at baseline and related to an underlying disease.

A significant clinically change is defined as follows: Pulse Rate < 40 or >100 bpm; systolic Blood Pressure < 90 or >160 mmHg; diastolic Blood Pressure > 100 mmHg.

Blood pressure and pulse rate will be measured after a rest of 10 minutes in supine position. Blood pressure will not be measured on the arm used for the injection.

 CONFIDENTIAL	Protocol No. GDX-44-008 Version No.4.0 including amendments 1 and 2 12 December 2017	Page 36 / 64
---	--	--------------

8. NUMBER OF SUBJECTS

As a proof of concept study, no statistical test is planned. Subjects' data will be analyzed with descriptive statistics investigating the potential efficacy of P03277 in the liver for the diagnosis of HCC, by dose.

In total 40 subjects will be included:

- Firstly, 30 subjects in a first cohort with a P03277 dose of 0.1 mmol/kg
- Then 10 subjects in a second cohort with a P03277 dose of 0.05 mmol/kg

Number of subjects for the first cohort of the study is based on the hypothesis supported by a meta-analysis of several publications (8) that among the 30 subjects with suspected nodules, around 66% would have a HCC and the remaining subjects would be negative (liver nodule proven as a non HCC) and or uncertain after biopsy. Those hypothetic figures would help to estimate sensitivity and specificity values with the limitations expected for such small sample size.

It is considered that 10 subjects included in the second cohort will be sufficient to have an exploratory evaluation of the diagnostic value based on sensitivity and specificity.

 CONFIDENTIAL	Protocol No. GDX-44-008 Version No.4.0 including amendments 1 and 2 12 December 2017	Page 37 / 64
---	--	--------------

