- **Hematology tests** by central lab at screening visit or inclusion visit and after administration at Day+1 for all subjects : Red Blood Cells (RBCs), White Blood Cells (WBCs), neutrophils, eosinophils, basophils, lymphocytes and monocytes, platelet count, hemoglobin, hematocrit, Mean red blood Cells Volume (MCV).
- **Tolerance at the injection site** will be recorded from time of administration of P03277 up to 30 minutes post administration and 1 day after injection.
- **Adverse event (AE)** will be recorded throughout the subject participation until the +1day safety FU. Only AE that the investigator considers as related to P03277 and/or the study procedures will be recorded at the optional Visit 4 between 3 days after P03277 administration up to 3 month.

Statistical methods:

For primary endpoint: descriptive analysis of P03277 MRI sensitivity and specificity results using standard of reference will be presented by dose.

Descriptive statistics will be provided for secondary efficacy endpoints will be presented by dose and clinical and biological safety and will presented by dose and overall.

 CONFIDENTIAL	Protocol No. GDX-44-008 Version No.4.0 including amendments 1 and 2 12 December 2017	Page 7 / 64
---	--	-------------

STUDY FLOW CHART

[figure not shown]
Visit	Screening (V1)	Inclusion and P03277 liver imaging visit (V2)					Safety follow-up (V3)	Biopsy /procedure for specimen histology (V4 optional as per standard of care)	
Timing	-7 to -0 days	Inclusion Day 0	Pre-injection	Dosing	Acquisition of triphasic MRI sequences	30mn	Optional very delayed acquisition	Day +1	Between 3 days after V2 and up to 13 weeks
Informed consent signature	x								
Eligibility criteria (1)	x	x							
Physical examination (2)	x								
Demographic data	x								
Medical history	x								
Chronic liver disease status	x								
Previous imaging results and AFP measurement collected for reference diagnosis	x	x							
Proposed diagnosis according to available examinations for standard reference (excluding histology and P03277 images)								x	
Biopsy histologic analysis for reference diagnosis (3)									x
Body weight		x							
Concomitant treatments	↔								
Pregnancy test (4)	x	x							
Vital signs (BP, HR) (5)	x	x				x		x	
Blood samples for laboratory parameters (6)	(x)	x						x	
e-GFR for screening (7)	x								
IP administration			x						
MRI examination (8)			x	x		(x)			
Injection-site tolerance (9)					↔		x		
Adverse events (AEs) (10)	↔								(x)

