For multiphasic MRI, GBCA were found to participate to the characterization of malignancy of nodules in the liver. Extracellular GBCA are used for their ability to show typical characteristics for HCC with 0.820 (95% CI 0.776, 0.857) of sensitivity in patients with any-sized lesions; and estimated specificities were 0.934 (95% CI 0.881, 0.964) according to a recent meta-analysis (6).

P03277 is a new chemical entity discovered and developed by Guerbet. It is a non-ionic macrocyclic gadolinium (Gd) complex intended to be used in human, by intravenous administration, as a contrast agent for MRI.

P03277 has a molecular weight of 970.11 g/mol. [REDACTED]

[REDACTED] P03277 is used as an aqueous injectable solution for injection at a concentration of 0.5 M.

The ability of P03277 to be a MR contrast agent has been demonstrated by at least two-fold higher T1 relaxivity compared to other available GBCAs. A proof of concept has been obtained for the efficacy of P03277 as a MR contrast agent for CNS imaging in a model of brain tumor (C6 glioma) implanted in rats. In this experimental brain tumor model, the dose of 0.1 mmol/kg of P03277 allowed for an increase in contrast enhancement of at least 30% as compared to other GBCAs administered at dose of 0.1 mmol/kg, including MultiHance® (highest relaxivity among the GBCA).

P03277 is a Gd chelate with a very high stability, limiting the risk of release of toxic free Gd in the body. The results of preclinical data indicate a good tolerance and a low toxicity profile at dose levels and exposure much higher than the anticipated clinical dose. This satisfactory tolerance has been confirmed in a phase I/IIa study. In this study, 36 healthy volunteers and 12 patients were administered with a single dose of P03277 and 18 volunteers with placebo. No serious adverse reaction occurred in any of these volunteers at any of tested dose at 0.025, 0.5, 0.75, 0.1, 0.2, and 0.3 mmol/kg BW. No clinically significant changes in vital signs or laboratory findings were noted.

In this phase I/IIa study, pharmacokinetics profile was shown to be dose-dependent (linear) that is the reason why only one dose is considered as needed for this new proof of concept study. [REDACTED]

[REDACTED]

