The aim of GDX-44-008 study is to explore the diagnostic value for HCC of P03277 triphasic imaging of suspected nodules in patients with liver diseases. Some small HCC usually showing atypical features may be better seen and characterized under imaging with P03277. Participating subjects will not directly benefit from P03277 MRI. They will be diagnosed according to a combination of examinations for standard of reference including imaging and/or histology analysis

Guerbet  CONFIDENTIAL	Protocol No. GDX-44-008 Version No.4.0 including amendments 1 and 2 12 December 2017	Page 24 / 64
--	--	--------------

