2. STUDY OBJECTIVES

2.1 Primary Objective

To evaluate the diagnostic value (specificity and sensitivity) for hepatocellular carcinoma of P03277 in patients with suspected small nodules and chronic liver disease.

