2.2 Secondary Objectives

To evaluate multiple quantitative and qualitative efficacy parameters and the safety (clinical and biological) profile of P03277 following single administration in suspected HCC patients

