3. STUDY DESIGN

3.1 Protocol Description

Dual center, exploratory, non randomized, open label, two cohorts, two doses, phase IIa study.

The standard of reference for diagnostic will be given by the site according to their standard of care and adapted from EASL/EORTC diagnostic criteria (7) and considering previous contrast enhanced imaging (CT and/or MRI) and/or biopsy specimen analysis given on-site and/or the more recent AFP results available.

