5.1 Investigational Medicinal Product: P03277

Name: P03277 [REDACTED]

Pharmaceutical form: vial of 20 ml

P03277 is an aqueous solution. Each vial contains 20 mL of solution presented as a sterile, clear, yellow, ready-to-use solution for injection.

Concentration: 0.5 M

P03277 dose per administration:

- 0.1 mmol/kg BW (corresponding to 0.2 mL/kg body weight) for the first cohort (30 subjects),
- 0.05 mmol/kg BW (corresponding to 0.1 mL/kg body weight) for the second cohort (10 subjects).

P03277 will be injected via a peripheral vein (the antecubital vein is preferred). The IV injection line will consist of a large bore indwelling catheter (at least 18 gauge).

Sufficient IMP must be allocated to one subject according to his/her body weight.

Route and method of administration: by intravenous (IV) bolus injection at 2 mL/s rate without dilution, followed by a 0.9% saline flush at same rate to ensure complete injection of the contrast medium.

The P03277 administration is to be performed by power injector in order to better control injection rate.

Please refer to the Investigator Brochure for more information on P03277.

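### Does the section 1 statement that one dose is enough undermine the second-dose cohort of 10 subjects?

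*Protocol*

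**What the plan says.** Section 1 of the protocol lists the dose levels given in the phase I/IIa study, reports a linear pharmacokinetic profile, and continues: "that is the reason why only one dose is considered as needed for this new proof of concept study". Blacked-out text follows directly.

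The rest of the protocol describes two doses. Section 3.1 calls it an "open label, two cohorts, two doses, phase IIa study". Section 5.1 gives 0.1 mmol/kg for the first 30 subjects and "0.05 mmol/kg BW (corresponding to 0.1 mL/kg body weight) for the second cohort (10 subjects"). The synopsis and section 8 repeat the same two cohorts and sizes.

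Section 8 bases the 30 on an expected HCC share of about 66%. For the other cohort it says only that "10 subjects included in the second cohort will be sufficient to have an exploratory evaluation of the diagnostic value based on sensitivity and specificity". The same section states that no statistical test is planned and that the data will be described by dose.

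The primary objective in section 2.1 reads: "To evaluate the diagnostic value (specificity and sensitivity) for hepatocellular carcinoma of P03277 in patients with suspected small nodules and chronic liver disease". Section 2.2 adds other efficacy parameters and the safety "profile of P03277 following single administration in suspected HCC patients". Neither mentions dose. The synopsis plans for the primary endpoint a "descriptive analysis of P03277 MRI sensitivity and specificity results using standard of reference will be presented by dose", and section 12.3 does the same.

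**The concern.** Three things seem not to fit together. The rationale says one dose is enough, yet the design uses two. Reading dose as number of injections does not remove the conflict: the sentence follows a list of levels and rests on linearity, which is an argument across levels. Next, the objectives pose no question about dose, although the primary results will appear in one column per dose. Last, 10 subjects are called sufficient with no expected split and no precision target, whereas the 30 at least come with an assumed HCC share.

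If these gaps were real, a quarter of the subjects would receive a dose with no stated question behind it, in a study about which section 1 says "Participating subjects will not directly benefit from P03277 MRI". A reader who set the two columns side by side as a dose comparison could draw conclusions that 10 subjects cannot support.

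**Working it through.** **1. Is the two-dose design itself consistent?**

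- Total: 30 + 10 = 40, as section 8 states. Second cohort: 10/40 = 25%.
- Volumes in section 5.1 at 0.5 M (0.5 mmol/mL): 0.1/0.5 = 0.2 mL/kg and 0.05/0.5 = 0.1 mL/kg, both as stated.
- Synopsis, 3.1, 5.1 and 8 agree on the number of cohorts; the synopsis, 5.1 and 8 also agree on the doses and sizes.

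The only visible outlier is the one sentence in section 1. It is background text: no instruction to a site, no eligibility rule and no analysis depends on it.

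**2. Does section 8 say what the 10 subjects are sufficient for?**

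- Section 8: an exploratory look at diagnostic value, measured by sensitivity and specificity.
- Section 2.1: diagnostic value, defined by the same two measures.

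The second cohort therefore applies the stated primary objective at a second dose. The figure of 10 cannot be reproduced from any formula, because the protocol gives no target rate, interval width or decision rule for it. It is a judgement and is presented as one.

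**3. Is a comparison between doses planned?**

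Section 8 plans no test. The synopsis and section 12.3 present efficacy by dose. No contrast, margin or selection criterion between doses appears in the protocol. The text describes two separate summaries.

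**4. How imprecise is the second cohort?**

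Assumption: the 66% HCC share, stated only for the first cohort, also holds in the second.

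- First cohort: 0.66 × 30 = 19.8 HCC; 0.34 × 30 = 10.2 non-HCC or uncertain.
- Second cohort: 0.66 × 10 = 6.6 HCC; 0.34 × 10 = 3.4 non-HCC or uncertain.

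The analysis unit is the nodule, with at most 3 per subject.

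- Nodules for sensitivity: 6.6 × 1 = 6.6 to 6.6 × 3 = 19.8.
- Nodules for specificity: 3.4 × 1 = 3.4 to 3.4 × 3 = 10.2. If each HCC subject also carried two non-HCC or uncertain nodules, up to 10.2 + 6.6 × 2 = 23.4.

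Effect of one wrong reading, 1/n:

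- Specificity: 1/3 = 33 points, 1/10 = 10 points, 1/23 = 4 points.
- Sensitivity: 1/7 = 14 points, 1/20 = 5 points.

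Exact (Clopper-Pearson) lower 95% limit for a perfect score, 0.025^(1/n), with nodules taken as independent (the best case):

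- 3/3: 29%; 7/7: 59%; 10/10: 69%; 20/20: 83%; 23/23: 85%.

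For scale, at one nodule per subject in the first cohort, 16/20 gives 56% to 94% and 9/10 gives 55% to 100%. The larger cohort is also imprecise, and section 8 acknowledges the limits of so small a sample there.

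**5. Do these figures measure the inconsistency?**

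No. Each depends only on the cohort size and the assumed HCC share. Rewording section 1, or adding a dose question to section 2, would leave every one of them unchanged.

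**The case for a change.** The strongest case for a change is that objectives belong in the protocol and are not something an analysis plan can supply. Section 2 is not blacked out and has no dose question. The correction looks cheap: one sentence each in sections 1, 2 and 8. With 10 subjects, the chance of 2 or fewer non-HCC or uncertain subjects is 28% (binomial, probability 0.34), so specificity at the second dose could rest on almost nothing, and a reader should be told in advance how to take it.

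Part of this stands. The visible section 1 sentence conflicts with the design, and the passages must be reconciled. A sentence on how to read the second column would also be courteous to the reader.

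The rest does not carry. Section 8 already gives the second cohort a purpose within the primary objective. The harm comes from a between-dose reading that the protocol does not plan; a stand-alone first look is the only use it describes. The sentence on lack of direct benefit covers all 40 subjects, so it marks no cost specific to the second cohort. Section 1, as far as it can be read, does not say which dose is the one needed, so it cannot be taken to call 0.05 mmol/kg unnecessary. Nor is the correction free: under section 14.2 a modified protocol goes back to the ethics committee and the competent authority, here for edits that alter no procedure and no result.

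**Conclusion.** No change to the plan follows. There is one wording inconsistency, in the rationale: the visible sentence in section 1 does not fit the two-cohort, two-dose design set out consistently in the synopsis and in sections 3.1, 5.1 and 8. These passages must be reconciled as a matter of editing. This note takes no view on how many doses, or which, are right. Because blacked-out text follows the sentence and the text of amendment 2 is also blacked out, a reason for the second dose may already be given there.

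The inconsistency has no effect on the results. Following the plan as written gives the same two descriptive summaries, 30 subjects and 10, whether or not the sentence is corrected. The second cohort's wide intervals (for a perfect score, a lower limit between 29% and 85% depending on the number of nodules) rest on the assumed 66% HCC share and on independent nodules. They call only for cautious reading of a small exploratory cohort.

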9. STUDY SCHEDULE AND PROCEDURES

9.1 Study Schedule

9.1.1 Screening Visit – Visit 1 – Day - 7 to Day 0

During this visit, the following tasks or assessments will be performed:

- A **written informed consent** will be obtained from the subject as described in [Section 14.3](#);
- The subject will be attributed an **Identification Number** as described in [Section 4.3](#);
- A **routine physical examination** (performed by a physician) including the examination of general appearance, skin, neck (including thyroid), eyes, ears, nose, throat, lungs, heart, abdomen, back, lymph nodes, extremities, vascular and neurological; Information indicating the global assessment (normal or abnormal (specify)) of the physical examination should be recorded on source documentation;
- A review and record of **concomitant treatments**;
- Recording of **demographic data** such as sex, age, measurement of height, ethnic origin (self-reported race/ethnicity).
- **Documentation of relevant medical history**/current medical condition present before signing the informed consent. The Investigator will also question on any possible previous contrast agents injection intolerance (type of agent : iodinated, gadolinium complex, barium, radiopharmaceutical, other specify) and report them in medical history;
- **Documentation of chronic liver disease history and status**: documentation supporting the diagnostic of chronic liver disease (biopsy, endoscopic, biological, ultrasound parameters, and elastography), aetiology of chronic liver disease (alcohol, HBV, HCV, non-alcoholic-NASH, other specify) and last evaluation of Child Pugh score ([see appendix 1](#)) available (including the date);
- **Documentation of suspected nodules** detection modality and date;
- **Examination results available for standard of reference diagnosis evaluation** per nodule before P03277 administration:
 - Liver map (according to Couinaud segmentation) identifying the localization of the nodule(s) (maximum of 3) for standard of reference
 - Size of the nodule (s) to be considered according to investigator's choice among the several imaging modalities
 - Contrast enhanced imaging modalities used for characterization (CT and/or MRI), type of contrast agent used for MRI (extracellular, hepatospecific), date of acquisition and, for each of nodules if HCC typical hallmark is visualized according to EASL/EORTC criteria and in case of MRI using hepatospecific contrast agent, also if hyperintensity of parenchyma relative to the nodule is seen.
 - The more recent AFP measurements available and date
- **Biopsy or intervention for specimen surgery** scheduled for histology analysis. The planned date should be recorded.
- A **urine or serum pregnancy test** for all women of childbearing potential should be done and must be negative;
- **Verification of eligibility criteria**. Criteria relative to eGFR measurement may not be available at screening ;

 CONFIDENTIAL	Protocol No. GDX-44-008 Version No.4.0 including amendments 1 and 2 12 December 2017	Page 38 / 64
---	--	--------------

- Schedule of **blood sample collection for serum creatinine** dosage if applicable, in order to obtain the results and calculate eGFR at the time of inclusion at the latest;
- If done at screening, **blood samples for baseline hematology/biochemistry tests** will be collected according to central laboratory manual. If not done at screening, they have to be scheduled at inclusion visit (V2).
- Recording the subject screening visit in the CRF.

9.1.2 Inclusion Visit – Visit 2 – Day 0

Inclusion visit can be the same day as screening if all eligibility criteria can be verified the same day.

During this visit, the following tasks or assessments will be performed:

- **Verification of inclusion and non-inclusion criteria** by the Investigator; creatinine results for eGFR calculation should be available before P03277 administration.
- **A urine or serum pregnancy test** for female subject of childbearing potential will be performed prior to P03277 administration and must be negative (do not perform the test if a negative pregnancy test result performed within 24 h prior to the MRI is available);
- Any changes in **concomitant treatments** since the last visit will be documented;
- **Any AE** occurred since the last visit will be documented
- If not already done at screening, **blood samples for baseline haematology/biochemistry tests** will be collected according to central laboratory manual;
- Measurement of **body weight**;
- **Vital signs** (systolic and diastolic Blood Pressure in supine position, Pulse Rate) will be recorded prior to contrast agent injection;
- One or two **IMP will be allocated** according to subject body weight;
- **The appropriate volume of P03277 will be administered** by IV as a bolus at the rate of 2 mL/second following a 0.9% saline flush at the same rate. The following information will be documented in the source document and reported on CRF pages: the location of the IV injection line, confirmation of power injector use and reason for not, actual volume injected and actual rate of the injection, and start time of injection, volume of saline flush, any reason for different rate than 2mL/s or different volumes of more than 10% than the calculated one;
- **Unenhanced and contrast-enhanced MRI** will be performed according to the required sequences specified in imaging protocol [section 9.2](#). Enhanced imaging sequences will be acquired according to imaging protocol and start time of each post injection sequences will be recorded. Any deviation from the specified MRI procedures and the reason for it (scanner-related problem or subject-related problem) will be also documented;
- **Vital signs** (systolic and diastolic Blood Pressure and PR) will be obtained 30 ± 5 minutes after the injection of P03277. If significant changes in vital signs occur, vital signs should be recorded more frequently and for as long as necessary, to ensure that the changes are resolved, and/or that the subject is stable;
- **Injection-site tolerance** (burning, pain, eruption, extravasation, inflammation, or other) is to be assessed during the injection and up to 30 minutes after the injection of P03277;

 CONFIDENTIAL	Protocol No. GDX-44-008 Version No.4.0 including amendments 1 and 2 12 December 2017	Page 39 / 64
---	--	--------------

- **Assessment of AEs** will be documented;
- Safety follow-up visit (Visit 3) needs to be scheduled 1 day post P03277 injection.

